## 14.0 BODY FLUID BIOSPECIMENS

Not Applicable

## 15.0 DRUG INFORMATION

### 15.1 Armodafinil (Nuvigil®) or placebo

#### 15.1.1 Background

Armodafinil indicated as adjunctive therapy in the treatment of obstructive sleep apnea (OSA) and to improve wakefulness in patients with narcolepsy and shift work disorder (SWD). Armodafinil is the R-enantiomer of modafinil, which is a mixture of the R- and S-enantiomers. The precise mechanisms through which armodafinil and modafinil promote wakefulness are unknown. Both agents have shown similar pharmacologic properties in nonclinical animal and *in vitro* studies.

- At pharmacologically relevant concentrations, armodafinil does not bind to or inhibit several receptors and enzymes potentially relevant for sleep/wake regulation. Armodafinil is not a direct- or indirect-acting dopamine receptor agonist. Armodafinil has wake-promoting actions similar to sympathomimetic agents, but the pharmacologic profile is not identical to that of the sympathomimetic amines.
- Armodafinil has been classified as a Schedule IV controlled substance. Investigators who prescribe this agent must have an up-to-date Controlled Substance Registration Certificate. The agent must be stored in compliance with state and federal regulations related to Schedule IV controlled substances.

#### 15.1.2 Formulation

Commercial armodafinil (Nuvigil®) tablets contain 50, 150 or 250 mg of armodafinil and the following inactive ingredients: croscarmellose sodium, lactose monohydrate, magnesium stearate, microcrystalline cellulose, povidone, and pregelatinized starch.

**15.1.3 Preparation and storage:**

Armodafinil (Nuvigil®) tablets are stored at 20° to 25°C (68° to 77°F)

**15.1.4 Administration:**

Armodafinil will be taken as a single dose in the morning. Food delays absorption, but this has minimal effects on bioavailability. Armodafinil may therefore be taken without regard to food intake. If the patient misses a dose, the tablet can be taken that day as long as it is atleast 12 hours before the next dose.

**15.1.5 Pharmacokinetic information:**

- a) Absorption – Readily absorbed.
- b) Distribution – $V_d$ : 42L. Approximately 60% protein bound, primarily to albumin (based on modafinil)
- c) Metabolism –Hepatic, via multiple pathways, including CYP3A4/5. Metabolites include R-modafinil acid and modafinil sulfone. Clearance is 33 mL/minute, mainly via hepatic metabolism. Half-life elimination is 15 hours. Steady state is reached at approximately 7 days. The time to peak concentration (fasting) is 2 hours.
- d) Excretion – Urinary (80%, predominantly as metabolites); < 10% as unchanged drug.

**15.1.6 Potential Drug Interactions:**

Armodafinil is a major substrate of CYP3A4. Dosage adjustment should be considered for concomitant medications that are substrates for CYP3A4/5, such as steroid contraceptives, triazolam, and cyclosporine. Armodafinil is a moderate inhibitor of CYP2C19. Drugs that are largely eliminated via CYP2C19 metabolism, such as diazepam, propranolol, and phenytoin may have prolonged elimination upon coadministration with armodafinil, and may require dosage reduction and monitoring for toxicity.

**15.1.7 Known potential toxicities**

The use of armodafinil is contraindicated in patients with hypersensitivity to armodafinil, modafinil, or any component of the formulation.

Use is not recommended in patients with a history of angina, cardiac ischemia, recent history of MI, left ventricular hypertrophy, or patients with mitral valve prolapse, who have developed mitral valve prolapse syndrome with previous CNS stimulant use.

Angioedema and hypersensitivity (with rash, dysphagia, and bronchospasm) have been observed with armodafinil. Small average increases in mean systolic and diastolic blood pressure were seen in patients with narcolepsy taking armodafinil when compared to placebo.

Serious and life-threatening rashes including Stevens-Johnson syndrome, toxic epidermal necrolysis, and drug rash with eosinophilia and systemic symptoms have been reported with modafinil, the racemate of armodafinil. Most cases have been reported within the first 5 weeks of therapy.

In pre-approval narcolepsy, OSA and SWD controlled trials of armodafinil, anxiety, agitation, nervousness, irritability, and depression were reasons for treatment

discontinuation more often than for placebo. Cases of suicide ideation were also observed in clinical trials.

The use of armodafinil may impair the ability to engage in potentially hazardous activities.

The agent should be administered at a reduced dose for patients with severe hepatic impairment. There is inadequate information to determine the safety and efficacy of dosing patients with severe renal impairment. Elimination of the agent and its metabolites may be reduced in elderly patients. Consideration should be given to the use of lower doses in this population.

Headaches are dose related and reported in > 10% of patients. Adverse reactions reported in 4 to 10% of patients include nausea (dose related), dizziness, insomnia (dose related), anxiety, and diarrhea. Adverse events reported in < 4% of patients include: depression (dose related), dyspepsia, fatigue, palpitations, rash (dose related), upper abdominal pain, agitation, anorexia, constipation, contact dermatitis, decreased appetite, depressed mood, attention disturbance, dyspnea hyperhidrosis, increased heart rate, flu-like syndrome, loose stools, migraine, nervousness, pain, paresthesia, polyuria, pyrexia, thirst, tremor, xerostomia (dose related), and vomiting.

#### **15.1.8 Study agent procurement**

Armodafinil 150mg and 250mg tablets will be purchased for use in this trial. The placebo tablets will be purchased from PharmOps Inc. Armodafinil and placebo will be bottled, labeled, and distributed by the Alliance research base pharmacy. The armodafinil/placebo will be provided in bottles containing 56 tablets.

Each participating Alliance main membership or each participating affiliate site will order *one* patient-specific bottle of blinded armodafinil/placebo from the research base pharmacy each time a patient is registered in the trial. Fax the completed Alliance Clinical Drug Order/Return Form to:

See protocol Appendix XI for specific instructions.

Outdated or remaining drug/product should be destroyed on-site per procedures in place at each institution.

#### **15.1.9 Nursing Guidelines**

- Patients must take drug in the morning, with or without breakfast.
- Headaches are possibility. Instruct patients to contact study staff if they develop new onset of headaches.
- Instruct patient to monitor for hypersensitivity reactions such as rash and itching. Patients should immediately report any signs of fever, spreading rash, or joint aches.

### **15.2 Placebo**

Placebo tablets will be purchased from PharmOps, Inc., Phillipsburg, NJ. The tablets will similar in appearance to the armodafinil tablets. The tablets will contain anhydrous lactose (bulking agent), microcrystalline cellulose (bulking agent/binder), crospovidone (disintegrant), and magnesium stearate (lubricant).

## 16.0 STATISTICAL CONSIDERATIONS AND METHODOLOGY

### 16.1 Study Design

This is a three-arm randomized clinical trial. The primary goal of this study is to compare the response rate of patients randomized to one of two doses of armodafinil or placebo in terms of a clinically meaningful improvement in patient-reported fatigue of at least a two-point improvement in the 0-10 point Brief Fatigue Inventory usual fatigue item at eight weeks post-treatment initiation. Endpoints will be assessed per arm and compared across arms by comparing each armodafinil arm versus the placebo arm in turn. We make no adjustment for multiple comparisons as we want to err on the side of moving forward the appropriate dose into phase III testing upon the basis of promising information in the proposed trial.

The three arm randomized trial will accrue a maximum of 330 patients to randomize a 100 evaluable patients per arm based on a binary endpoint to armodafinil or placebo.

Bayesian adaptive “shadow” design: Bayes clinical trial designs are becomingly increasingly more popular as alternatives to classic Fisherian designs, especially in the phase I context (110). They have not, however, been applied to cancer control cooperative group clinical trials. As a feasibility exercise, we will use the results of this trial to “shadow” what would have happened if the Bayes design would have been used. This will provide us insights into the relative utility of the Bayes design within the context of cooperative group cancer control clinical trials. The potential advantage of the Bayes approach is that the study likelihood of efficacy is constantly monitored allowing for the possibility of early study completion and therefore a smaller number of patients put at risk (see MD Anderson Cancer Center Technical Report UTMDABTR-002-06 (98). There are a number of logistical and statistical issues that were raised in the review of the concept (which initially proposed a Bayes design) that we decided it would be more prudent to use a classic Fisherian design to run the trial and use a shadow design to obtain preliminary data for planning future cancer control clinical trials using a Bayes approach. The details for the Bayes design are attached as Appendix X.

### 16.2 Sample Size

On average, we recruit six patients per month for GBM treatment trials. For symptom control studies with heterogeneous populations, such as N05C7 (Concerta), we were able to average 25 patients a month. We have found that symptom management trials targeting symptoms with a high prevalence have rapid accrual. Therefore, for this study, a reasonable conservative estimate for this more homogeneous population would be 8 patients a month. With 330 patients, accrual would be completed in 41 months.

The randomized design to be utilized is described below. Based on our previous work, we estimate that the response rate for the placebo arm will be 10%. We design the study with 100 patients per arm so that the Fisher’s exact test will have 80% power to detect a response rate of 25% with a two-tailed alternative and a 5% Type I error rate for each treatment comparison to the placebo. Again, we are not using a conservative multiple contrasts approach because we want to err on the side of accepting a modest armodafinil effect. We plan to accrue an additional 30 patients to account for patient cancellations, ineligibility, or major treatment violations. Therefore, there will be a maximum of 330 patients accrued to this study unless undue adverse events are encountered.

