### 16.3 Primary Endpoint

The primary endpoint of this trial is the response rate in terms of a clinically meaningful improvement in patient-reported fatigue at 8 weeks. A response is defined as an improvement of 2 points on the 0-10 scale of the usual fatigue on the BFI.

All patients meeting the eligibility criteria who have signed a consent form, have begun treatment, and have not had a major treatment violation within the 1st cycle of treatment will be evaluable for the primary endpoint. Patients will be analyzed according to the arm in which they were randomized.

Comparison of the primary endpoint between arms will be based on a binomial point estimate computed for each arm and a Fisher's exact test will be the inferential hypothesis test.

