## 16.5 Statistical Design

The primary endpoint for the trial is the response rate in terms of a clinically meaningful improvement in patient-reported fatigue, defined as at least a two-point improvement in fatigue as measured by the usual fatigue item from the Brief Fatigue Inventory at 8 weeks. This change

will be from baseline to 8 weeks (after randomization). The design proposed for this study will randomize a maximum of 330 evaluable patients to one of three treatment arms.

**Efficacy stopping rules:** This study will be monitored by Alliance Data and Safety Monitoring Board (DSMB) every 6 months for safety and efficacy. If at any time prior to full accrual the p-value for the Fisher's exact test that an arm is superior to the other arm given all available data falls below 0.001 then consideration will be given to stopping the trial early.

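### Section 16.2 claims 80% power for Fisher's exact test at 100 per arm (25% vs 10%); the exact figure is 76.2%

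*Combined protocol and SAP*

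**What the plan says.** Section 16.2 bases the sample size on one power statement. For the placebo rate it says "we estimate that the response rate for the placebo arm will be 10" percent. With 100 patients per arm, Fisher's exact test "will have 80% power to detect a response rate of 25% with a two-tailed alternative and a 5% Type I error rate", and that error rate applies separately to each dose's comparison with placebo. Section 16.1 confirms that there is no adjustment for multiple comparisons. Section 16.3 names the same test for the primary analysis: Fisher's "exact test will be the inferential hypothesis test".

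Three sections describe the number of patients. Section 16.1 says the trial "will accrue a maximum of 330 patients to randomize a 100 evaluable patients per arm". Section 16.2 explains the margin: "We plan to accrue an additional 30 patients to account for patient cancellations, ineligibility, or major treatment violations". Section 16.5 says something different: "The design proposed for this study will randomize a maximum of 330 evaluable patients to one of three treatment arms".

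**The concern.** Fisher's exact test is conservative when response rates are low, so a sample size of exactly 100 per arm for 10% vs 25% looks like the result of a normal-approximation formula rather than of the test named in the plan. If so, the stated power belongs to a test that will not be used.

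Power is the plan's stated reason for 100 per arm. An overstated figure means that a negative dose comparison is read against a smaller risk of a missed effect than the design carries. It also runs against the aim in Sections 16.1 and 16.2, which is to lean towards carrying a modestly effective dose forward. Section 16.5 makes the basis harder to identify, because 330 evaluable patients would be 110 per arm, not 100.

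**Working it through.** **Inputs.** All come from Section 16.2: placebo rate 0.10; active rate 0.25; 100 per arm; two-sided α = 0.05 per comparison; Fisher's exact test; stated power 80%. Section 16.1 (no multiplicity adjustment) leaves α at 0.05.

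**1. Where 80% can be reproduced.** The uncorrected pooled-variance normal formula is

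n = [z₀.₉₇₅·√(2·p̄·(1−p̄)) + z₀.₈₀·√(p₁(1−p₁) + p₂(1−p₂))]² / (p₂−p₁)²

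with p̄ = 0.175. Putting the numbers in:

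- First term: 1.960 × √0.28875 = 1.0532
- Second term: 0.8416 × √(0.09 + 0.1875) = 0.4434
- n = (1.4965)² / 0.15² = 2.2397 / 0.0225 = 99.5, which rounds up to 100 per arm

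The same approximation at n = 100 gives 80.2% power. This matches the plan's figure, but it is not Fisher's test.

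**2. Power of the test the plan names.** Let X be the number of responders on the active dose, Binomial(100, 0.25), and Y the number on placebo, Binomial(100, 0.10). Then

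Power = Σₓ Σᵧ P(X = x)·P(Y = y)·1[Fisher two-sided p(x, y) ≤ 0.05]

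where the p-value sums the probabilities of all tables no more probable than the one observed. Results at 10% vs 25%:

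| n per arm | Power |
|---|---|
| 100 | 76.2% |
| 105 | 78.0% |
| 109 | 79.95% |
| 110 | 80.4% |

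A simulation of 400,000 trials at 100 per arm gives 76.1%. Doubling the one-sided p-value, the other common two-sided definition, also gives 76.2%, so the gap does not depend on the definition.

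**3. Why the two tests differ.** Take 20 vs 10 responders out of 100 each. The uncorrected test gives z = 0.10/√(2 × 0.15 × 0.85/100) = 1.98, p = 0.048, and rejects. Fisher's p-value is 0.073, and it does not reject. When both true rates are 10%, Fisher's test rejects 2.9% of the time rather than 5%.

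**4. Other routes to 80% at n = 100.** The exact power of the uncorrected chi-square test is 81.6%, and of mid-p Fisher 80.5%. Fisher's test at one-sided 5% gives 84.8%. None of these is the test specified. The continuity-corrected formula, which mimics Fisher's test, gives 74.5% at 100 per arm and asks for 113 per arm.

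**5. What 100 per arm can detect with 80% power.** With placebo at 10%, power is 79.6% for an active rate of 25.7% and 80.05% for 25.8%. The detectable rate is about 25.8%.

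**6. The extra 30 patients.** With equal allocation, 330 accrued is 110 per arm. If all 30 are lost, as Section 16.2 allows, 100 per arm remain and power is 76.2%. If none are lost, 110 per arm remain and power is 80.4%. Only the Section 16.5 wording, with all 330 evaluable, supports 80%.

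**The case against.** The arithmetic is not in dispute; the case against concerns how much it matters.

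- **Small next to the uncertainty in the placebo rate.** That rate is itself an estimate. Against a true 25% at 100 per arm, Fisher power is 80.4% if placebo is 9.4%, 68.5% if it is 11% and 60.2% if it is 12%. A 0.6-point shift in a planning guess would close the gap. This stands as a reason to call the shortfall modest. It does not make 80% correct for the 10% that the plan uses.
- **The trial tests two doses.** If both truly reach 25%, the chance that at least one comparison is significant is about 89%, ignoring interim looks. That is true, but the plan's 80% is stated per comparison, and so is the 76.2%.
- **76.2% is not a floor.** The Section 16.3 definition of an evaluable patient does not require a week-8 fatigue score. If a complete-case analysis had 95 observed outcomes per arm, power would be 73.9%; with 90 it would be 70.9%. These losses are illustrative, because the plan gives no dropout rate. The calculation also leaves out the p < 0.001 efficacy looks (Section 16.5) and possible closure of the 250 mg arm (Section 16.7.1). These caveats apply equally to the plan's own sentence.
- **The test could be changed instead.** Prespecifying the uncorrected chi-square test would deliver at least the stated 80% at the same sample size. This is a legitimate option for the sponsor, but it changes the primary analysis, whereas restating the power does not.
- **The Section 16.5 wording is a separate slip.** Sections 16.1 and 16.2 agree with each other and settle the intended numbers. The power error stands without it, but one edit can repair both.

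**Conclusion.** The concern holds. The power in Section 16.2 does not belong to the test, rates and sample size given in the same sentence: it should be 76.2% rather than 80%, a shortfall of 3.8 points per comparison. The risk of missing a true 25% response rate is 100% − 76.2% = 23.8%. The result rests on the plan's own inputs, with a primary outcome available for all 100 patients in each arm and no allowance for interim looks. That the 80% came from the normal approximation is an inference from the matching sample size; the plan gives no source. The stated figure should be corrected, but the shortfall does not undermine the design.

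**What to change.** Change two sentences.

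1. **Section 16.2.** Restate the power, for example: *Fisher's exact test with 100 evaluable patients per arm has about 76% power for 25% vs 10% (80% power for about 25.8% vs 10%), two-sided 5% per comparison.* Adding that this assumes a week-8 outcome for every evaluable patient would make the condition explicit. Keep Fisher's exact test as the primary test.
2. **Section 16.5.** Bring it into line with 16.1 and 16.2: up to 330 patients accrued, of whom 300 (100 per arm) are planned to be evaluable.

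The cost is wording only, with no change to patients, test or decision rules. Keeping 80% power for 25% vs 10% with Fisher's test would instead need 110 evaluable per arm, or 330 evaluable in all. At the planned loss of 30 in 330, accrual becomes 330/(300/330) = 363 patients. At 8 per month that is 363/8 = 45.4 months, against 330/8 = 41.3 months now. The restatement avoids that cost.

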In an open-label trial conducted to evaluate the benefit of modafinil in managing CRF, patients who had completed treatment for breast cancer (chemotherapy, chemotherapy and/or radiation therapy), received modafinil 200 mg daily for 1 month (56). Upon completion of treatment with modafinil, mean fatigue severity decreased from 6.9 to 3.7 (0-10 scale: 0 = fatigue not present and 10 = fatigue as bad as you can imagine). The mean rating on the patient-reported global effectiveness measured after therapy was 5.0 (with 1 = no benefit and 7 = great improvement). This benefit rating supports the finding that participants perceived an improvement in fatigue with the use of open label modafinil. Furthermore, 51% of the patients reported improvement in sleep and 51% reported less daytime drowsiness. Additional benefits reported by a majority of patients (>60%) included improvements in general activity, mood, walking ability, normal work ability, relations with other people, and enjoyment of life. Four patients withdrew from the study: 1 due to pregnancy and 3 due to "agitation" that developed after 1 week of treatment.

Morrow et al (57) conducted a second open-label trial of modafinil, with the same purpose as the previous trial, in women with breast cancer who experienced fatigue levels of 2 or more on the Brief Fatigue Inventory (0-10 scale, 0 = no fatigue and 10 = fatigue as bad as it can be) at least 1 month following completion of radiation therapy. Patients received modafinil 200 mg once daily for 1 month. Of the 82 women enrolled, 76 completed the study. Reasons for discontinuation were pregnancy (n = 1), anxiety (n = 2), headache (n = 2), and nausea (n = 1). Ninety percent of the women experienced an improvement in fatigue.

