## 13.0 TREATMENT/FOLLOW-UP DECISION AT EVALUATION OF PATIENT

If the patient discontinues the study agent prior to 8 weeks, the patient will go off study.

A patient is deemed *ineligible* if after registration, it is determined that at the time of registration, the patient did not satisfy each and every eligibility criteria for study entry. If the patient received treatment, all data up until the point of confirmation of ineligibility must be submitted. If the patient never received treatment, on-study material must be submitted.

A patient is deemed a *major violation*, if protocol requirements regarding treatment in cycle 1 of the initial therapy are severely violated that evaluability for primary end point is questionable. All data up until the point of confirmation of a major violation must be submitted.

A patient is deemed a *cancel* if he/she is removed from the study for any reason before any study treatment is given. On-study material and the End of Active Treatment/Cancel Notification Form must be submitted. No further data submission is necessary.

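### The over-accrual of 30 does not cover patients who start drug and leave before week 8, so the 80% power is not shown for patients with an observed week-8 BFI

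*Combined protocol and SAP*

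**What the plan says.** Section 16.2 sets the size: "We design the study with 100 patients per arm". The power claim, made for the Fisher procedure, is that this design "will have 80% power to detect a response rate of 25% with a two-tailed alternative and a 5% Type I error rate for each" of the two comparisons with placebo. The planning rates are 10% on placebo and 25% on armodafinil. Section 16.1 gives the same target: "The three arm randomized trial will accrue a maximum of 330 patients to randomize a 100 evaluable patients per arm". The difference between 330 and 300 is explained in 16.2: "We plan to accrue an additional 30 patients to account for patient cancellations, ineligibility, or major treatment violations".

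Section 13.0 defines the three named losses. A cancel is removed before any study treatment. An ineligible patient failed an entry criterion at registration. A major violation is a severe breach of the cycle 1 treatment requirements. The same section adds: "If the patient discontinues the study agent prior to 8 weeks, the patient will go off study".

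Section 16.3 defines the evaluable set: "All patients meeting the eligibility criteria who have signed a consent form, have begun treatment", and no major violation in cycle 1. A week-8 BFI is not a condition, although the endpoint is response at week 8. Section 16.8 lists complete-case analysis and several imputations, names none as primary, and gives no expected missing rate.

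**The concern.** A patient who starts drug, follows the protocol and leaves in weeks 1 to 8 falls into none of the three categories for which the 30 places are held. The protocol itself provides routes to that exit. Section 8.0 stops the agent for related toxicity of grade 3 or worse, or at the patient's discretion regarding toxicity. Section 9.0 takes off study anyone who begins another fatigue treatment. The BFI is scheduled only at baseline, week 4 and week 8 (4.0, 11.1), and no week-8 collection is described for patients who are off study.

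Such a patient is evaluable under 16.3 but has no observed response. One hundred evaluable patients per arm is therefore not the same as 100 patients with the primary outcome, and 16.2 computes power as if it were. Section 16.1 uses the result to decide which dose moves to phase III. A null comparison run at 60 to 70% power should not be read as one run at 80%.

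**Working it through.** **Inputs from the documents.** Placebo 10%, active 25%, two-sided 5% per comparison, 100 per arm, Fisher's exact test (16.2, 16.3); 330 accrued, so 110 per arm (16.1).

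**Assumed input.** Loss before week 8, d, among patients who start. The one completion count with a denominator in the cited modafinil studies is in 1.2.2: "Of the 82 women enrolled, 76 completed the study", that is 6/82 = 7% over one month in breast cancer. I take 7%, 14% (twice that, for two months), 20% and 30%.

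**Step 1: the plan's own figure.** The pooled two-proportion formula without continuity correction, with mean rate 0.175, gives

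z = [0.15·√100 − 1.96·√(2·0.175·0.825)] / √(0.10·0.90 + 0.25·0.75) = 0.848, so power = 80.2%.

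The 80% reproduces. Full enumeration of the two-sided Fisher test, which is the test named, gives 76.2% at 100 per arm with no loss. It first reaches 80% at 110 per arm (80.4%). That gap has nothing to do with drop-out.

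**Step 2: losses dropped.** Fisher power at n per arm, 10% vs 25%.

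| Loss d | 30 fully used: n = 100(1−d) | Power | None of the 30 used: n = 110(1−d) | Power |
|---|---|---|---|---|
| 0% | 100 | 76.2% | 110 | 80.4% |
| 7% | 93 | 72.7% | 102 | 77.2% |
| 14% | 86 | 68.3% | – | – |
| 20% | 80 | 64.8% | 88 | 69.6% |
| 30% | 70 | 58.4% | – | – |

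**Step 3: losses counted as non-responders.** Keep 100 per arm. *If* 10% and 25% are rates among completers, both are multiplied by (1−d).

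| Loss d | Rates compared | Power |
|---|---|---|
| 7% | 9.3% vs 23.25% | 72.2% |
| 14% | 8.6% vs 21.5% | 67.8% |
| 20% | 8% vs 20% | 63.5% |
| 30% | 7% vs 17.5% | 55.6% |

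With unequal loss, 10% on placebo and 20% on active, the rates become 0.10·0.90 = 9% and 0.25·0.80 = 20%, and power is 53.9%. If the planning rates already treat drop-outs as failures, the comparison stays 10% vs 25% at 100 per arm and power stays at 76.2%.

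**Step 4: does unequal loss always hurt most?** If losses are dropped at random, 90 placebo vs 80 active gives 71.0%. An equal 15% loss (85 per arm) gives 67.7%. So it does not.

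**The case against.** The best defence is that 30 is a round allowance with no rates attached. A reader might infer that the margin is used up by its three named purposes, but nothing in the documents says so. Unused places would absorb drop-out: at 7% loss, 110 starters leave 102 with an outcome and 77.2% power, slightly above the 76.2% at a full 100. On the plan's pooled formula, 110 starters keep 80% up to about 9–10% loss (81.7% at 5%, 79.8% at 10%). This stands, and it is why both margins are shown. It does not supply the missing allowance: under the Fisher test, 80% requires that none of the 30 is used and nobody leaves.

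Second, 16.3 keeps every treated, eligible patient without a major violation in the denominator, and 16.2 rests the 10% on previous work without saying how drop-outs were scored there. If they were scored as failures, no power is lost. The documents do not settle this.

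Third, 16.8 offers last-value carry-forward, and a week-4 BFI is scheduled, so a patient leaving in weeks 5 to 8 could be classified. True, but no method is named as primary, so the effect on power is undefined.

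Fourth, although 3.1 admits ECOG status up to 3, it also requires clinical stability and a stable corticosteroid dose. The higher loss rates are assumptions, not predictions.

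**Conclusion.** The omission is certain; its size is not. The losses named in 16.2 exclude ordinary post-start drop-out by the definitions in 13.0, and the 80% is stated for a number that 16.3 does not tie to an observed week-8 BFI.

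Measured from the Fisher baseline of 76.2%, with the margin fully used, the part due to drop-out is about 4 points at 7% loss (76.2 − 72.7 = 3.5 dropped; 76.2 − 72.2 = 4.0 as non-responders) and 11 to 13 points at 20% (11.4 and 12.7). With the margin wholly unused and losses dropped, power is 77.2% at 7% and 69.6% at 20%. The non-responder figures hold only if 10% and 25% are completer rates.

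Two stronger readings are tempting. One charges the whole fall from 80% to drop-out; the first 3.8 points come from using the uncorrected formula in place of Fisher's test. The other holds that power falls most when a dose causes more drop-out. That is seen here only under the non-responder rule, the 10-point difference behind the 53.9% has no source in the documents, and Step 4 shows the reverse when losses are dropped. This should be corrected, but it does not show that the trial is too small by any known amount.

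**What to change.** **In 16.2:** add loss of the week-8 outcome to the listed losses. State the expected number per arm with a week-8 BFI. Restate the Fisher power for that number over a stated range of losses, for example 7%, 15% and 25%. Say whether 10% and 25% already count drop-outs as non-responders.

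**In 16.3 and 16.8:** name which listed missing-data method is primary for the responder endpoint, keep the others as sensitivity analyses, and separate being evaluable from having a week-8 BFI.

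**Cost:** wording only. No extra patients are required; the price is a less favourable stated power. Restating does not restore power. If the sponsor wanted 100 per arm with an observed outcome while keeping the 30/330 loss, accrual would be 3 × 100/(1−d)/(1−30/330), rounded up per arm: 369 at 10% loss and 414 at 20%. That is a choice, not a condition of this point.
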